4.10.3 Analysis of Secondary Efficacy Endpoints / Variables

Definitions of secondary efficacy endpoints / variables are found in Section 3.2.1.2; they will be analyzed for the ITT Analysis Set.

4.10.3.1 Analysis of Progression Free Survival by Central Review

PFS (see Section 3.2.1.2) by central review will be summarized descriptively and graphically using Kaplan Meier methods. The Kaplan Meier survival estimates, together with the number of subjects, percentage of subjects to experience the event, and the number and percentage of subjects censored will be summarized by treatment group. If data warrant, the Kaplan-Meier estimate for the median progression free survival time and the first and third quartiles will be determined along with 95% CIs using the Brookmeyer-Crowley method. For the analysis of PFS, the PD assessment by central review will be used to determine the status and date of events for PFS regardless of treatment discontinuation.

[name] S.A	
Protocol RI-01-006	Statistical Analysis Plan

A by-subject listing will be provided for central review as well as investigator assessed PFS by treatment group.

Table 11 provides the detailed event/censoring rules for statistical analysis of PFS.

 Table 11 Event/Censoring Rules for PFS Analysis

Situation	Date	Outcome
No baseline tumor assessment	Date of randomization	Censored
PD or death at or before next scheduled assessment	Date of the first radiological tumor assessment demonstrating PD, or date of death	Progressed
New anticancer treatment started without documented PD	Date of last radiological tumor assessment prior to initiation of new therapy	Censored
PD or death after more than one missing assessments	Date of the last radiological tumor assessment prior to the missing assessments	Censored
No PD and no death	Date of the last radiological tumor assessment	Censored
Death before first PD assessment	Date of death	Progressed
Death between adequate assessment visits	Date of death	Progressed

For the Week 28 CSR analysis, subjects will be administratively censored at Week 28 if no progression or other censoring appeared prior to Week 28.

4.10.3.2 Analysis of Overall Response by Central Review at Week 12 and at Week 28

OR by central review at Week 12 and at Week 28 will be summarized using frequencies, percentages and corresponding 95% CIs by treatment group.

4.10.3.3 Analysis of Complete Response by Central Review at Week 28

Complete response (CR) by central review at Week 28 will be summarized using frequency, percentage and corresponding 95% CI by treatment group.

4.10.3.4 Analysis of Complete Response by Central Review up to Week 28

Complete response (CR) by central review up to Week 28 will be summarized by using frequency, percentage and corresponding 95% CI by treatment group.

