8.2 Efficacy Assessments

The primary endpoint for efficacy is BORR, defined, as the proportion of subjects in each treatment group that achieve a best overall response of either CR, CRu or PR up to Month 7 (Week 28) based on central radiology review in accordance with the response criteria for malignant lymphoma.¹³ This necessitates the use of bone marrow biopsies if bone marrow was involved at Screening or any abnormality occurred during treatment; combined PET-CT scans are not required

for this version of the response criteria, but are allowed if the CT portion has the slice thickness compatible with spiral CT scans.

Disease assessments are to be performed as scheduled according to Table 1–1, regardless of treatment delays resulting from toxicity. Care must be taken in scheduling disease assessments to prevent the introduction of bias based on treatment delays. Failure to perform any of the required disease assessments will result in the inability to determine disease status for the impacted time point. A series of incomplete disease assessments will result in inability to determine disease response status and censoring of PFS back to the time of the last full assessment that did not show progression. Frequently off-schedule or incomplete disease assessments have the potential to weaken the conclusion of this clinical study.

Assessments are NOT to be scheduled based on the previous imaging time point, but rather Day 1 should be used as the baseline when calculating when the on-study tumour assessments are to be performed (with consideration of visit windows). The CT scans should be performed with contrast agents, unless contraindicated for medical reasons. If i.v contrast is medically contraindicated, imaging without contrast can be used. Depending on the adequacy for evaluation of disease, a combination of CT without contrast and magnetic resonance imaging should most often be used. Such cases will be reviewed by the medical team, and their inclusion in the Per Protocol (PP) Population will be discussed at the blinded data review meeting(s).

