1 INTRODUCTION

[name] (DRL) is developing a proposed biosimilar version of the chimeric anti-CD20 monoclonal antibody (mAb), rituximab (DRL_RI). DRL_RI is a chimeric human/murine IgG1 kappa mAb consisting of murine light and heavy chain variable regions and human constant region sequences. The molecule is composed of two heavy chains of 451 amino acids each and two light chains of 213 amino acids each with a molecular weight of 145 kDa. Each of the heavy chains contains one N-linked glycan (resulting in 2 N-linked glycans per molecule).

This document describes planned statistical analyses as well as the rules and conventions to be used in the presentation of efficacy, safety, pharmacokinetics, pharmacodynamics, and immunogenicity data for [name] S.A.'s "Randomised, Double-blind, Parallel-group, Phase III Study to Compare the Efficacy, Safety, and Immunogenicity of Proposed Rituximab Biosimilar (DRL_RI) with MabThera[®] in Subjects with Previously Untreated, Stage II-IV, Cluster of Differentiation (CD)20 Positive, Low Tumour Burden Follicular Lymphoma".

This Statistical Analysis Plan (SAP) is applicable for unblinded statistical analysis of all data up to Week 28, and for the statistical analysis of all data up to Week 52 after database lock and general unblinding after the end of the study.

For the purposes of analysis, the study will be unblinded to specified Sponsor/designee members (refer to the latest version of Blinding Maintenance Plan (BMP)) – but not investigators or subjects – once all subjects have reached Week 28 (or earlier termination of study). All individuals with access to unblinded data and analysis results up to Week 28 will sign a confidentiality agreement to maintain the study blind up to general unblinding after final database lock. For the Week 28 CSR analysis, all data up to Week 28 (\pm 7 days, the allowed visit window for the Week 28 visit) will be included. Analysis for the Week 52 CSR will be prepared after database lock and general unblinding after study closure.

The analyses described in this SAP are based upon the following study documents:

- Clinical Study Protocol RI-01-006, version 5.0 (27 October 2021)
- Electronic Case Report Form (eCRF), Version 9.0 (21 March 2022).

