3.2 Definition of Endpoints / Variables

3.2.1 Definition of Efficacy Endpoints / Variables

3.2.1.1 Definition of the Primary Efficacy Endpoint / Variable

BOR up to Week 28 is defined as the best overall response at any radiologic tumor evaluations (based on central radiology review applying the Cheson 1999² response criteria for malignant lymphoma) up to the end of the allowed window for the Week 28 evaluations. Unscheduled and early termination evaluations will be only considered if they are complete and performed up to the end of the allowed window for the Week 28 evaluations.

[name] S.A	
Protocol RI-01-006	

The primary efficacy endpoint used in the statistical analysis is a binary (response / non-response) BOR up to Week 28 version is defined below. The impact of Intercurrent Events on binary BOR up to Week 28 is not described here but in Section 4.10.2.

For subjects with known tumor response at both Week 12 and Week 28, the definition of binary version of BOR up to Week 28 (the primary efficacy endpoint in the statistical analysis) is:

Response at Week 12	Response at Week 28	Binary version of BOR up to Week 28
CR, CRu or PR	Any known	Response
Any Known	CR, CRu or PR	Response
SD or PD	SD or PD	Non-Response

For subjects with a missing / unknown ("unknown" covers "not evaluable", "not available", "subject not anymore in the study", etc.) tumor response at Week 12 or at Week 28 and tumor response known at the other time-point, the definition of binary version of BOR up to Week 28 is:

Response at Week 12	Response at Week 28	Binary version of BOR up to Week 28
CR, CRu or PR	Missing / Unknown	Response
Missing / Unknown	CR, CRu or PR	Response
SD or PD	Missing / Unknown	Non-Response
Missing / Unknown	SD or PD	Non-Response

For subjects with only missing / unknown tumor responses, the definition of binary version of BOR up to Week 28 is:

Response at Week 12	Response at Week 28	Binary version of BOR up to Week 28
Missing / Unknown	Missing / Unknown	• Non-Response for main analysis using the exact score method, sensitivity analysis using stratified Mantel- Haenszel method, and FDA main estimand
		• Missing for sensitivity analyses within the estimand framework (except FDA main estimand) using multiple imputation approaches and for supplementary analyses as described in Section 4.10.2.3

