Appendix 5 Visit Windowing Rule for Tumor Assessments

Table 16 Visit Windowing Rule for Tumor Assessment

Visit	Start day	Target Day	End Day
Baseline	1	1	1
Week 12	56	84	112
Week 28	168	196	224
Week 52/EOS	336	364	392

Note: Subject who prematurely terminated from the study will be mapped to correct visit based on target day.

CONFIDENTIAL

PAREXEL International Electronic Signature Page

This page is the manifestation of the electronic signature(s) used in compliance with PAREXEL International's electronic signature policies and procedures and in compliance with applicable regulations.

UserName: PPD PPD

Date: Friday, 26 August 2022, 12:24 PM GMT Standard Time Meaning: Document contents authored.

UserName: PPD PPD

Date: Friday, 26 August 2022, 12:25 PM GMT Standard Time Meaning: Document contents approved.

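### The Week 28 report cuts PFS at an undefined Week 28, so progressions first seen on later in-window Week 28 scans can be lost as PFS events while the same scans count for response and DOR

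*SAP*

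**What the plan says.** Four SAP rules bear on Week 28 tumour data in the first report.

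- **PFS (4.10.3.1).** Table 11 dates progression at the first scan that shows it. Its row for event-free subjects reads "No PD and no death Date of the last radiological tumor assessment Censored". One sentence is then added for the Week 28 report: "subjects will be administratively censored at Week 28 if no progression or other censoring appeared prior to Week 28". It gives no day number and does not say how it ranks against Table 11.
- **Tumour windows (Appendix 5, "Visit Windowing Rule for Tumor Assessment").** The rows give start, target and end day: "Week 12 56 84 112" and "Week 28 168 196 224".
- **Data cut (section 1).** The report takes data up to Week 28 ± 7 days, described as "the allowed visit window for the Week 28 visit) will be included".
- **Other endpoints.** BOR uses scans "up to the end of the allowed window for the Week 28 evaluations" (3.2.1.1). The main DOR summary (4.10.3.6) has a cut-off no earlier than the last Week 28 evaluation in any subject and uses Table 11. A further DOR summary is cut at each subject's own Week 28 visit.

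For a series of incomplete assessments, Protocol 8.2 calls for "censoring of PFS back to the time of the last full assessment that did not show progression".

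**The concern.** Scans are scheduled at Weeks 12 and 28, so the Week 28 scan is half of the scheduled on-study imaging behind the first report. A rule that recognises only progression *before* Week 28 cuts through the middle of the window for that scan. A progression read centrally on an in-window scan can then be in the database, be used for response, end a response for DOR, and yet appear as a censored observation for PFS.

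At stake are the numbers and percentages of subjects with a PFS event and censored, which 4.10.3.1 requires by arm, and the agreement between tables built from the same scans. A programmer would also have to choose both the cut day and the order of precedence.

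**Working it through.** **1. The window.** 28 × 7 = 196; 196 − 28 = 168; 196 + 28 = 224. This reproduces the Appendix 5 row. Week 12: 84 ± 28 = 56 to 112. The ±7 day visit window is Days 189 to 203 (15 days); the tumour window is Days 168 to 224 (57 days).

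**2. Which day is Week 28?** Appendix 5 supports Day 196; the section 1 data cut supports Day 203. Extending the induction labels in 4.2.6 (Week 2 is Day 8) would give 7 × 27 + 1 = Day 190. Day 196 is the only one stated as a target for tumour assessments.

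**3. Share of Week 28 scans past the cut**, assuming scan days evenly spread:

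| Reading | ±7 day window | ±28 day window |
|---|---|---|
| Day 196, that day kept | 7/15 = 47% | 28/57 = 49% |
| Strictly before Day 196 | 8/15 = 53% | 29/57 = 51% |
| Day 203 | 0/15 = 0% | 21/57 = 37% |

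**4. Events lost.** The documents give no progression or missing-scan rates. Assume 2% progress at Week 12, a proportion r = 3% to 10% at Week 28, and m = 5% to 10% without a Week 28 scan.

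- Week 28 progressions = 312 × 0.98 × r × (1 − m). Low: 312 × 0.98 × 0.03 × 0.90 = 8.3. High: 312 × 0.98 × 0.10 × 0.95 = 29.0.
- All PFS events, adding 312 × 0.02 = 6.2 at Week 12: 14.5 to about 35.
- Lost at Day 196 (that day kept): 8.3 × 7/15 = 3.9 up to 29.0 × 28/57 = 14.3.
- Lost at Day 203, ±28 day window: 8.3 × 21/57 = 3.0 up to 29.0 × 21/57 = 10.7. In the ±7 day window: none.

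Simulation under the same assumptions (300 replicates per setting) agrees: about 15 to 36 events with every Week 28 scan, about 11 to 22 with a Day 196 cut.

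**5. The curve.** With Table 11 otherwise kept, the Day 196 cut is plain truncation. Simulated Kaplan-Meier at Day 196 was 0.91 to 0.96 both with and without it.

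**6. One subject, four rules.** Take PR on Day 84 and first PD on Day 210.

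- Response: the scan lies in the Appendix 5 window, so it is used.
- Main DOR summary: an event on Day 210.
- PFS cut at Day 196: censored.
- PFS cut at Day 203: the progression is not included.

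With PD on Day 200, the Day 203 cut keeps the PFS event and the Day 196 cut loses it.

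**7. Precedence.** Take an event-free subject last scanned on Day 84. If Table 11's last-scan row counts as other censoring, censoring stays at Day 84 and no time is gained. If the administrative sentence overrides the row, the subject is carried to Day 196: 196 − 84 = 112 days (196 − 112 = 84 to 196 − 56 = 140 over the Week 12 window).

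**The case against.** The strongest reply is that section 1 already states the data cut. Read with it, the PFS rule runs to Day 203 and loses no scan done within the ±7 day visit schedule. That stands for on-schedule scans. It does not cover scans on Days 204 to 224, which Appendix 5 still assigns to Week 28, and 4.10.3.1 does not refer to section 1.

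The allowed window in 3.2.1.1 might also mean ±7 days. The conflict with the primary endpoint on Days 204 to 224 would then vanish, but the conflict with the main DOR summary would remain.

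Third, Week 28 could mean each subject's own Week 28 evaluation. That would remove the loss. The DOR section has wording tied to the evaluations and visits; the PFS sentence has none.

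Two stronger readings are tempting, and the documents support neither.

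- A reader might infer that every subject without a Week 28 scan is credited with about 16 event-free weeks. The sentence exempts subjects with other censoring before Week 28, and Table 11 already censors them at the last scan. The credit arises only if the sentence overrides the table, which the SAP does not say. Protocol 8.2 points towards the last scan.
- A reader might infer that the PFS curve is too favourable and any difference between arms compressed. Truncation leaves the estimate before the cut unchanged. Only under the override reading did the simulated curve rise, to 0.93 to 0.97 just before Day 196, and no effect on the difference between arms was shown.

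**Conclusion.** The point holds as a conflict between stated rules with a definite effect on counts. Followed literally, the PFS rule gives too few events and too many censored subjects in the Week 28 report, and can disagree with DOR and response from the same scans. The loss is about half of Week 28 progressions at a Day 196 cut. At a Day 203 cut it is none to 37%, depending on how far scans spread beyond ±7 days. In events, that is about 4 to 14 and 0 to 11 respectively, resting on even scan timing and the assumed rates above. The precedence question is open, not a demonstrated error.

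The consequence is small. PFS is a descriptive secondary endpoint without a test or margin, the rule is the same in both arms, and the equivalence decision on BOR does not use it. Protocol 9.4.7 makes secondary endpoints optional in the first report and updates time-to-event endpoints in the addendum, so the Week 52 analysis recovers the events.

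**What to change.** Replace the administrative sentence in SAP 4.10.3.1. For the Week 28 report, PFS should include progression or death up to each subject's Week 28 evaluation or the end of its tumour window (Day 224); name one of the two. Events are dated by Table 11. All other subjects are censored at their last adequate scan by that cut-off, and Table 11 takes precedence.

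Then align the ±7 day data cut in section 1 for tumour assessments, and the DOR cut-off in 4.10.3.6, with the same definition. The OS section (4.10.3.5) carries the same administrative sentence. Deaths are dated directly, so the scan problem does not arise there, but its Week 28 also needs a day.

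The cost is a few SAP sentences and one cut-off variable in the programs, with no new data collection. Deleting the PFS sentence alone would not be enough, because section 1 would still exclude Days 204 to 224. The edit belongs before the Week 28 unblinding.

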2.3 Benefit/Risk Assessment

There is a substantial body of data related to the safety and efficacy of Rituxan[®]/MabThera[®] in subjects with B-cell NHL (Food and Drug Administration [FDA] Rituxan[®] prescribing information/European Medicines Agency [EMA] MabThera[®] SmPC).^{1,2} A comprehensive head-to-head comparison of [name] rituximab antibody, DRL_RI, to the US-approved Rituxan[®], and the European RMP (MabThera[®]) has demonstrated that DRL_RI is similar to Rituxan[®] and the RMP (Section 2.2.4.2). Thus, the risk/benefit of DRL_RI is expected to be comparable to that of Rituxan[®]/MabThera[®].

More detailed information about the known and expected benefits and risks and reasonably expected adverse events (AEs) of DRL_RI may be found in the IB for DRL_RI.¹¹

3 Objectives and Endpoints

Objective	Endpoint			
Primary				
To demonstrate the equivalent efficacy of DRL_RI and MabThera [®] in subjects with B-lymphocyte antigen CD20-positive, LTB-FL, as measured by ORR up to Week 28, evaluated in accordance with published response criteria for malignant lymphoma.	The primary endpoint is BORR, defined as the proportion of subjects in each treatment group that achieve a best overall response of either CR, CRu or PR up to Month 7 (Week 28) based on central radiology review in accordance with the response criteria for malignant lymphoma. ¹³			
Secondary				
• To compare the ORR at Week 12 and Week 28, CR at Week 28, CR as a best response up to week 28, duration of response (DOR), PFS and OS of DRL_RI with MabThera [®] in subjects with CD20-positive, LTB-FL.	 Overall response rate at Week 12 and Week 28 based on central radiology review in accordance with published response criteria for malignant lymphoma¹³. Complete Response (CR) rate at Month 7 (Week 28). CR rate as a best response up to Month 7 (Week 28). Duration of response defined as the time from date of the first documentation of tumour response (CR, CRu or PR) to the date of first documentation of PD or to death due to any cause up to 52 weeks/EOS. Progression-free survival defined as the time from date of randomisation to the date of documented progressive disease (PD) or death due to any cause. Overall survival defined as the time from date of randomisation to the date of Study (EOS). 			

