2.2 Secondary Objectives

Secondary objectives are:

- To compare overall response (OR) at Week 12 and Week 28, CR at Week 28, CR as a best response up to Week 28, duration of response (DOR), PFS and OS of DRL_RI with MabThera[®] in subjects with CD20-positive LTB-FL
- To compare safety, tolerability, and immunogenicity of DRL_RI with MabThera[®] in subjects with CD20-positive, LTB-FL

[name] S.A Protocol RI-01-006

Statistical Analysis Plan

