4.10.3.5 Analysis of Overall Survival

OS will be summarized descriptively and graphically using Kaplan Meier methods. The Kaplan Meier survival estimates, together with the number of subjects, percentage of subjects to experience the event,

[name] S.A	
Protocol RI-01-006	

and the number and percentage of subjects censored will be summarized by treatment group. If data warrant, the Kaplan-Meier estimate for the median overall survival time and the first and third quartiles will be determined along with 95% CIs using the Brookmeyer-Crowley method.

A by-subject listing will be provided for OS by treatment group.

If a subject is not known to have died at the time of analysis cut-off, OS will be censored at the date of last contact. For example, if information of death is still pending or unknown under clinical operation and could not be obtained this information during the dry run analysis, then the last contact date will be considered as censored date of overall survival analysis. For the Week 28 CSR analysis, subjects will be administratively censored at Week 28 if no death or other censoring appeared prior to Week 28.

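### The secondary objective is to compare the two arms, but the SAP plans only per-arm summaries and no between-arm estimate or interval for any secondary efficacy endpoint

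*SAP*

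**What the plan says.** **Objective.** SAP 2.2 reads "To compare overall response (OR) at Week 12 and Week 28, CR at Week 28, CR as a best response up to Week 28" and continues with DOR, PFS and OS of DRL_RI with MabThera. Protocol Section 3 uses the same verb: "To compare the ORR at Week 12 and Week 28, CR at Week 28, CR as a best response up to week 28".

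**Planned analysis.**
- Response at Weeks 12 and 28 (SAP 4.10.3.2): "OR by central review at Week 12 and at Week 28 will be summarized using frequencies, percentages and corresponding 95% CIs by treatment group".
- CR at Week 28 (SAP 4.10.3.3): "Complete response (CR) by central review at Week 28 will be summarized using frequency, percentage and corresponding 95% CI by treatment group".
- Best CR (SAP 4.10.3.4): "Complete response (CR) by central review up to Week 28 will be summarized by using frequency, percentage and corresponding 95% CI by treatment group".
- PFS (SAP 4.10.3.1): "by central review will be summarized descriptively and graphically using Kaplan Meier methods".
- OS (SAP 4.10.3.5): "OS will be summarized descriptively and graphically using Kaplan Meier methods". DOR (SAP 4.10.3.6) is handled the same way.

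For the three time-to-event endpoints, medians and quartiles get Brookmeyer-Crowley 95% intervals where the data allow, again within each arm. Protocol 9.4.1.2 is also arm by arm and leaves further detail to the SAP.

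**Where the plan does estimate a contrast.** SAP 4.10.2.1 gives the DRL_RI minus MabThera difference in best overall response (BOR) with 90% and 95% exact score intervals. SAP 4.10.1.6 repeats this by subgroup in forest plots. SAP 4.12.2 gives a between-arm ratio of geometric means with intervals for AUEC, an exploratory marker.

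**The concern.** An objective worded as a comparison would normally be matched by an estimate of the contrast and its uncertainty. Here, subgroups of the primary endpoint and an exploratory pharmacodynamic marker have one, and the named secondary comparisons do not.

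The gap matters most for response at Week 28. Under the derivation tables in SAP 3.2.1.1, a subject with CR, CRu or PR at Week 12 counts as a response whatever the known Week 28 result, progression included. BOR therefore cannot show a difference between arms in early loss of response. Response at the fixed Week 28 time point can, and it has no planned between-arm estimate. Without one, a reader has two per-arm intervals to set side by side, and their overlap is a cruder guide than an interval for the difference.

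**Working it through.** **1. Endpoint-by-endpoint check.**

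| Endpoint | Per-arm output | Between-arm estimate |
|---|---|---|
| Response, Week 12 | n, %, 95% CI | none |
| Response, Week 28 | n, %, 95% CI | none |
| CR, Week 28 | n, %, 95% CI | none |
| Best CR to Week 28 | n, %, 95% CI | none |
| DOR | Kaplan-Meier | none |
| PFS | Kaplan-Meier | none |
| OS | Kaplan-Meier | none |

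SAP 4.2.9 sets interval levels and decimals but adds no contrast. SAP 4.14, on changes from the protocol, mentions no dropped comparison. SAP 4.10.3.1 to 4.10.3.6 carry no redaction marks, so the gap is not a product of blacked-out text.

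**2. The plan's own figures.** The documents give no precision or power figure for a secondary endpoint. The 312 subjects (156 per group, SAP 4.13.2) were sized for the primary endpoint, and the inputs to that calculation are not in the public text. The 156 is used below only as the arm size.

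**3. Precision of the missing binary contrasts.** Assumed rates, equal in both arms: 88% response (expected reference rate in SAP 4.10.2.3.4, and the published maintenance arm in protocol 2.2.3) and 60% CR+CRu (same published arm). All 156 per arm are taken as observed.

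- Per-arm 95% half-width = 1.96 × √(p(1−p)/156)
- Difference half-width = z × √(2p(1−p)/156), with z = 1.96 (95%) or 1.645 (90%)

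At 88%: 1.96 × √(2 × 0.88 × 0.12/156) = 1.96 × 0.0368 = 0.072.
At 60%: 1.96 × √(2 × 0.60 × 0.40/156) = 1.96 × 0.0555 = 0.109.

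| Rate | Per-arm 95% | Difference 95% | Difference 90% |
|---|---|---|---|
| 88% | ±5.1 | ±7.2 | ±6.1 |
| 75% | ±6.8 | ±9.6 | ±8.1 |
| 60% | ±7.7 | ±10.9 | ±9.1 |
| 45% | ±7.8 | ±11.0 | ±9.3 |

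The 60% includes CRu, while the SAP's secondary endpoint names CR only, so the 45% and 75% rows are given as a range. With fewer observed subjects, n per arm, the half-widths grow by √(156/n).

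**4. What overlap can hide (assumed rates).** Suppose Week 28 response is 75% on DRL_RI and 85% on MabThera. The per-arm 95% intervals are 68.2 to 81.8 and 79.4 to 90.6, which overlap. The difference is −10 points with standard error √(0.75 × 0.25/156 + 0.85 × 0.15/156) = 0.0449. Its 95% interval is −18.8 to −1.2 and its 90% interval −17.4 to −2.6. Both exclude zero, which the per-arm display does not show.

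**5. PFS.** SE(log HR) ≈ 2/√events. The event count is assumed, since the documents give none. At 30 events, exp(1.96 × 2/√30) = 2.05, about a factor of 2 each way. At 5%, 10% or 20% of 312 with an event, the 95% interval around a hazard ratio of 1 is 0.37 to 2.70, 0.50 to 2.02 or 0.61 to 1.64.

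**The case against.** The best defence is that the SAP's own usage lets comparison mean side-by-side description. SAP 4.12.2 says that time to B-cell depletion and repletion are compared descriptively through Kaplan-Meier curves and per-arm median intervals, the format used for PFS, OS and DOR. The parallel objective on safety and immunogenicity is also met descriptively. Descriptive secondary analysis suits a trial with one confirmatory endpoint and no multiplicity scheme (SAP 4.10.1.4). With counts reported per arm, a reader can compute the difference and its interval.

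Most of this stands. A reader might infer that the plan has no secondary intervals at all, or that it fails its secondary objective outright. The documents support neither: per-arm intervals are specified, and the objective can be read as descriptive. The excess of the summed per-arm half-widths over the half-width of the difference is only √2, as in any trial with equal arms, and shows nothing peculiar to this one.

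A reader might also infer that every secondary endpoint needs a formal contrast. That goes too far.
- DOR exists only in responders, as SAP 4.10.3.6 itself cautions, so a contrast would not be a randomised comparison.
- A hazard ratio stratified by the 18 randomisation strata (SAP 4.10.2.2.1) is not workable at an assumed 30 events: 30/18 is under two events per stratum.
- Scans at Weeks 12, 28 and 52 would leave progression times heavily tied.

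The defence does not explain why BOR subgroups and AUEC get a planned between-arm interval while Week 28 response does not. An interval that readers derive for themselves is also not prespecified, least of all in its treatment of missing responses.

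**Conclusion.** The point holds in a limited form. The objective speaks of comparing the arms, and for none of the seven secondary efficacy endpoints does the SAP specify a between-arm estimate or interval. It would be wrong to infer that the equivalence conclusion is at risk: the primary analysis of BOR is untouched, and no decision rule rests on a secondary contrast.

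The practical loss is mainly in the binary endpoints, and chiefly in Week 28 response, which can show early loss of response where BOR cannot. An interval of about ±7 points for response and ±11 for CR (95%) would be informative. These sizes rest on the Wald approximation, equal rates, the assumed 88% and 60%, and complete data on 156 per arm. Exact score intervals will differ somewhat. For PFS, the contrast would be too imprecise to be more than optional. The change is worth making, but it is not critical.

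**What to change.** In SAP 4.10.3.2 to 4.10.3.4, for response at Week 12, response at Week 28, CR at Week 28 and best CR, add the DRL_RI minus MabThera difference with two-sided 90% and 95% CIs by the unstratified exact score method of SAP 4.10.2.1, in the ITT Analysis Set.

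State how missing responses count. SAP 4.10.3 names the ITT set, while SAP 4.10.1.3 bases non-primary endpoints on observed data and SAP 4.2.2 takes subjects with data as the denominator. The primary main analysis instead sets subjects with no response evaluation to non-response. Best CR is also said to be derived much as BOR is (SAP 3.2.1.2), so the rule needs stating there too.

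Label these results descriptive and draw no equivalence conclusion from them. The 17-point margin is specified for BOR only.

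Optionally, add an unstratified descriptive PFS hazard ratio with 95% CI, noting its imprecision and the tied scan times. No DOR contrast is asked for.

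The cost is a few table rows, using a method already planned for the primary endpoint. With no decision rule attached, no multiplicity adjustment is needed. If the sponsor prefers to keep the arm-by-arm output, the minimum is to reword the objective as descriptive. That removes the mismatch but leaves Week 28 response without a direct estimate.
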